3.3 Exploratory Objective

The clinical utility of a test is related to the value-added it has for patient management. A test has utility if its results (positive or negative) provide valuable information to the patient and the provider in making decisions about effective clinical care. It can take the form of improved efficiency in clinical decision making, streamlined clinical workflow, better patient outcomes, and/or cost offsets or avoidance.

The level of clinical utility evidence required will likely depend upon a variety of factors, including the current Standard of Care (SOC), the setting of care, and potential cost offsets to mitigate the added cost of care, as well as the magnitude of the cost of the test itself.

The VIOLA Study is primarily concerned with the use of Melody®, its impact on mammography screening rates, and the overall participation in the breast health continuum of care. Proving Melody's® clinical utility through effective clinical outcomes, economically efficient implementation, and adoptability in a workflow is crucial for incorporating the Standard of Care.

4. Study Design and Endpoints

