4.2.3 Exploratory Endpoint

A widely accepted definition of clinical utility for an assay is that the assay results lead to a clinical decision with a high level of evidence to improve patient outcomes (11). Step one, Melody®, provides accurate diagnostic screening information. Step two, Melody's® results, when used in managing patients, given the benefits and harms, improves health outcomes in a clinically perceivable way compared with alternative management strategies. Melody® is proven useful if its results are actionable, driving a treatment decision that leads to a better outcome.

In a broad sense, the utility may be as simple as showing that Melody® provides equivalent or increased sensitivity and specificity, leading to equivalent or improved management decisions. Melody® is less invasive or incurs less patient harm. Melody® is less costly, providing, at minimum, the same benefit with fewer resources. Melody® is more widely or readily available than current screening options. Thus, more likely to be used to make patient management decisions across a more significant number of women. Does the clinical utility of Melody® increase participation in the breast health continuum of care?

5. Study Enrollment and Withdrawal

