7.3.3 Follow-Up / Final Study Visit

Follow-up Visit (Assessment of Study Endpoints / Safety)

- Site-specific procedures and instructions provided to participants to review assay results: Melody® Scale, Score, and Classification.

Script-reporting results

*I received your test results back, and your Melody® classification is **** (High or Low), and your score is***.*

*According to the scale provided by Namida Lab, Inc., in the range, you fall into of *** to *** ***percent of women had breast cancer and ****were normal.*

(It is up to you and your practice's discretion to make recommendations for the next steps in screening)

*This practice follows the *** guidelines, and for a woman of your age and family history, we recommend a screening mammogram.*

(If your practice typically schedules screening mammograms on behalf of patients, you may offer to do that now.)

A member of the Namida Lab, Inc. clinical team will reach out to you with the next steps for the VIOLA Study.

Final Study Visit

- Site-specific procedures and instructions are provided to participants to complete the exit questionnaire(s).
- Site-specific final instructions to the participant if additional care is required.

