10.4.5 Adherence and retention analysis

During the participant's journey through the study, there are various points where adherence and retention can be assessed. A log will be generated for each site listing each participant who has enrolled, their contact information, and where they are in the study process.

1. Study enrollment - A list can be generated by the site of participants enrolled. In addition, participants can be tracked via Namida Lab, Inc.'s LIMS system, as an open order will be generated once the participant's enrollment is complete.
2. Sample collection - Once the participant has completed sample collection at their site, the order will be completed, and the sample received by the lab.
3. Exit survey - A notification method will be arranged by site, which will allow site personnel to alert Namida Lab, Inc. when the results have been reported to study participants. Once this has occurred, the participant will be sent an exit survey.
4. After completing the exit survey, the study participant will receive the \$25.00 Walmart

gift card incentive. This will allow the study sponsor to track adherence and retention.

11. Source Documents and Access to Source Data/Documents

A Case Report Form will be completed for each participant enrolled in the clinical study. The investigator-sponsor will review, approve, and sign/date each completed CRF; the investigator-sponsor's signature serves as an attestation of the investigator-sponsor's responsibility for ensuring that all clinical and laboratory data are entered into the CRF are complete, accurate, and authentic. Any missing or spurious data will be accompanied by a note to file in the participant's record, which will clarify its reason and any action taken afterward.

Source Data are the clinical findings and observations, laboratory and test data, and other information in Source Documents. Source Documents are the original records (and certified copies of original records); including, but not limited to, all consent forms, app screens, app-based screening forms, regulatory documents, hospital medical records, physician or office charts, physician or nursing notes, participant diaries or evaluation checklists, pharmacy dispensing records, recorded data from automated instruments, x-rays, etc. When applicable, information recorded on the CRF shall match the Source Data recorded on the Source Documents.

12. Quality Assurance and Quality Control

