 Contraceptive Patch
 Intrauterine device (IUD)
 Vaginal Ring
 None
2. Are you currently using any hormone replacement therapy? (select one)
 Yes No
3. Please select what hormones you are currently taking: (select all that apply)
 Testosterone
 Estrogen
 Progesterone
 Other: _____
4. Hormone replacement medication name if known: _____
5. At what age did your periods begin? _____ (number)
6. Do you still have regular periods? (select one)
 Yes No
7. If you Do Not have regular periods, please select one of the following reasons: (select one)
 Menopause
 Hysterectomy
 Response to Birth Control
 Uterine Ablation
 Other (please describe): _____
 Unknown
8. Do you still have ovaries? (select one)
 Yes No

Section 3: Breast health:

1. Have you ever been told you have dense breast tissue? (select one)
 Yes No
2. Are you currently on, or have you been told, you should be on a high-risk breast cancer screening protocol? (select one)
 Yes No

3. Do you get an annual mammogram for breast cancer screening? (select one)
 Yes No
4. Do you get a bi-annual, every two years, mammogram for breast cancer screening? (select one)
 Yes No
5. When was your last screening mammogram? (enter date or select one)
(mm/dd/yyyy) ____/____/____ Unknown N/A
6. Have you ever received an abnormal screening mammogram? (select one)
 Yes No
7. From your last mammogram, what BI-RADS assessment category was on your mammogram results report? (select one)
 0 - Incomplete - Additional imaging evaluation and comparison to prior mammograms are needed.
 1 - Negative
 2 - Benign (non-cancerous findings)
 3 - Probably benign finding (follow-up in a short time frame is suggested)
 4 - Suspicious abnormality (biopsy should be considered)
 4A - Finding with a low likelihood of being cancer (more than 2% but no more than 10%)
 4B - Finding with a moderate likelihood of being cancer (more than 10% but no more than 50%)
 4C - Finding with a high likelihood of being cancer (more than 50% but less than 95%), but not as high as Category 5
 5 - Highly suggestive of malignancy (appropriate action should be taken)
 6 - Known biopsy-proven malignancy (appropriate action should be taken)
 Unknown

Section 4: Personal history and family history of cancer:

1. Please list below any cancers you have or have had in your lifetime.

No personal history of cancer Personal history unknown

Cancer Type	Year of diagnosis	Treatment	Treatment ongoing

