6. How would you rate your understanding of the Melody® report? (circle one)

Very Difficult	Somewhat Difficult	Somewhat Easy	Very Easy
1	2	3	4

7. How comfortable were you communicating the Melody® lab results back to patients? (circle one)

Very Uncomfortable	Uncomfortable	Comfortable	Very Comfortable
1	2	3	4

8. How did you relay results to the participant? (choose one)

- Over the phone
- In-person consultation
- Telemedicine visit
- Other: _____

9. How would you rate your understanding of how to use the Melody® classification and score?
(circle one)

Very Difficult	Somewhat Difficult	Somewhat Easy	Very Easy
1	2	3	4

10. How would you rate the usefulness of the information provided from Melody® in guiding your patients to make decisions about their breast health? (circle one)

Unacceptable	Poor	Fair	Excellent
1	2	3	4

11. How comfortable would you feel recommending this test to your patients in the future? (circle one)

Very Uncomfortable	Uncomfortable	Comfortable	Very Comfortable
1	2	3	4

12. As a provider, how many study participants did you **strongly recommend** they receive a screening mammogram after reviewing their Melody® results? _____ (number)

13. As a provider, how many study participants did you **recommend** they receive an annual screening mammogram after reviewing their Melody® results? _____ (number)

14. As a provider, how many study participants did you **recommend** they receive a bi-annual screening mammogram after reviewing their Melody® results? _____ (number)

15. How many study participants scheduled a screening mammogram after receiving a consultation about their Melody® result? _____ (number)

L. Namida Lab, Inc. Power Analysis (Sample Size)

Namida Lab ([name]) - Power Analysis

This power analysis contains several pieces. First, we give you some technical information about understanding effect size and how it relates to your needed sample size. We also included information about how the effect size relates to your study. Then, the table shows you the sample size needed at various effect sizes. Remember, the greater the difference you expect to see between your groups or the stronger the correlation, the larger your effect is and thus, the smaller the sample size you need in order to detect it.

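### Provider survey items 12-14 (Appendix K) collect overlapping, unlinked totals, so the study cannot tell from them whether recommendations differed by Melody result

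*Protocol*

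**What the plan says.** Appendix K is completed by the provider at exit, and its header carries only the site and the site's principal investigator. Item 12 asks for the number of participants strongly recommended a screening mammogram after their result was reviewed. Item 13 asks how many were recommended that "they receive an annual screening mammogram after reviewing their Melody® results", and item 14 how many that "they receive a bi-annual screening mammogram after reviewing their Melody® results". Item 8 allows one answer for how results were delivered, whatever the number of women. The number of results reviewed is not asked, and nothing is split by High or Low.

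The participant form (Appendix D, Section 3, item 4) defines the two-yearly interval: "Do you get a bi-annual, every two years, mammogram for breast cancer screening". Item 14 of the provider form uses the word without that definition.

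On utility, Section 3.3 (Exploratory Objective) states: "A test has utility if its results (positive or negative) provide valuable information to the patient and the provider in making decisions". Section 4.2.3 (Exploratory Endpoint) states: "Melody® is proven useful if its results are actionable, driving a treatment decision that leads to a better outcome". The results script in Section 7.3.3 contains the line "for a woman of your age and family history, we recommend a screening mammogram", with the same wording for High and Low. Section 10.4.5, step 3, says that a method will be arranged by site for personnel to "alert Namida Lab, Inc. when the results have been reported to study participants".

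**The concern.** If the result informs what the provider does, recommendations should differ between women classified High and women classified Low. Appendix K is the only instrument shown that records what providers recommended, and it records pooled totals. A total does not say which women it contains, how many it was drawn from, or whether the same women also appear in another item. The same three numbers can come from a clinic that acted on every result and from one that ignored them all.

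At stake is the provider strand of the exploratory utility objective. An analysis plan written later cannot repair this, because it cannot rebuild a link to the result that was never collected.

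**Working it through.** **Inputs.** The minimum of 205 women is from Section 5.3 and Appendix L. The 46% false-positive rate is from Sections 2.1 and 2.3.1. The 50 healthy controls behind it are in Section 2.1 and Table 2. Three or more sites are planned (Protocol Summary). The share of High results among study women is not given. I assume almost all are cancer-free, so that it is close to 46%.

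**The plan's own figure.** For 0.50 versus 0.70, two-sided 0.05 and power 0.80, n per group = [1.960·√(2·0.6·0.4) + 0.842·√(0.25 + 0.21)]² / 0.20² = 93, so 186 in total. Then 186 × 1.10 = 204.6, or 205. The figure reproduces and is not in dispute; it serves here only as the number of women.

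**1. Link to the result.** 205 × 0.46 = 94.3, so about 94 High and 111 Low. Suppose item 12 totals 94 across all forms.
- Every High and no Low woman strongly advised: 94/94 − 0/111 = +100 points.
- Same rate in both groups: 43/94 (45.7%) and 51/111 (45.9%), also 94 women, difference about 0.
- No High woman strongly advised: 0/94 − 94/111 = −85 points.

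In general, with H High, L Low and a total T, the number x of High women in the total can be anything from max(0, T − L) to min(H, T), and the difference is x/H − (T − x)/L.

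**2. Does this depend on 46%?** A simple 95% interval from 50 controls is 0.46 ± 1.96·√(0.46·0.54/50) = 0.32 to 0.60, or 66 to 123 High women. With T = 94:
- H = 66, L = 139: from −94/139 = −68 to 1 − 28/139 = +80 points.
- H = 123, L = 82: from 12/123 − 1 = −90 to 94/123 = +76 points.

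The sign is not identified in any of these cases.

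**3. Overlap.** Suppose all 205 women get one interval recommendation and 94 of them get it strongly. If providers put each woman in one item only, items 12 to 14 sum to 205. If they count strength and interval separately, the sum is 205 + 94 = 299. The care is the same in both cases.

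**4. Denominator.** Take one site of 68 women (205/3) with assumed totals of 30, 40 and 15 for items 12, 13 and 14. The number of distinct women given any recommendation lies between 40 and 68, or between 55 (40 + 15) and 68 if items 13 and 14 exclude each other.

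**5. What a per-woman record would give.** The High-Low difference would be estimable. Its widest 95% half-width, treating women as independent, is 1.96·√(0.25/94 + 0.25/111) = 13.7 points. For one overall proportion it is 1.96·√(0.25/205) = 6.8 points. Recommendations cluster within provider or site: with 3 clusters of 68 and an assumed intracluster correlation of 0.01 to 0.05, the design effect 1 + 67·ICC is 1.67 to 4.35, and 6.8 becomes about 9 to 14 points.

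**The case against.** The strongest reply is that little rests on these items. Sections 3.3 and 4.2.3 are exploratory and list several forms of utility, among them efficiency, workflow, cost, invasiveness and availability. Section 4.2.3 closes by asking about participation. The stated hypotheses concern participation against 2019, and no analysis in Section 10 uses items 12-14. This stands, and it limits the point to one exploratory strand.

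A reader might infer more than the documents support:
- **That the study cannot establish provider behaviour at all.** Section 11 requires a case report form for each participant and names physician notes and office charts as source documents. The form is not shown, so a recommendation field cannot be ruled out; none is described. The site log in Section 10.4.5 could supply a site-level denominator, though it cures neither the overlap nor the missing link.
- **That the totals merely show which guideline a clinic follows.** The script leaves next steps to the practice's discretion, and the sample report in Appendix I words its advice differently above and below the 0.1 threshold. Routine advice may dominate the totals, but that is not established.
- **That providers will read bi-annual as twice a year.** Section 3.2 pairs annual with bi-annual, and Appendix D defines the latter as every two years. The twice-yearly reading is strained; the missing definition is only a wording gap.
- **That double counting is certain.** The form sets strongly recommend against recommend, so a provider may treat them as exclusive. Overlap is possible, and nothing on the form says which reading applies.

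**Conclusion.** The point holds in limited form and the form should be changed. Items 12-14, as worded, cannot show whether provider recommendations differed by Melody result. With 94 of 205 women assumed High, one item 12 total of 94 is compatible with differences from −85 to +100 points, including 0, and the sign stays unidentified across the 66 to 123 High women that the validation sample allows. The conclusion about the form rests on its wording; the sizes rest on the assumed High share and the chosen total. The form also asks for no recommendation made before the result, so the items cannot show change either. The primary participation question and the sample size are untouched.

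**What to change.** Replace items 8 and 12-14 of Appendix K with a short per-participant entry keyed to the participant ID. Complete it when the site notifies the sponsor that the result was reported (Section 10.4.5, step 3) or on the participant's case report form. It should record:
- one interval recommendation from mutually exclusive options, including none;
- a separate yes/no for strongly recommended;
- the route by which the result was given.

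Write *every two years* for *bi-annual*, as the participant form defines it. Report recommendations by High versus Low over all women with a reported result, with a 95% confidence interval that allows for clustering by provider or site. With as few as three sites, a comparison stratified by site is safer than a cluster-robust standard error with sites as clusters.

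A field for what the practice's guideline would give without Melody may be added if it is completed before the result is opened. Filled in afterwards, it is retrospective self-report and should be labelled so. The entry records what was decided and prescribes nothing.

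The cost is a form amendment and a little site time per woman. Step 3 describes a method still to be arranged by site, so the entry has to be built into it or into the case report form; no existing form is described that could simply be extended.

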5.3 Strategies for Recruitment and Retention

Target sample size:

- An a priori power analysis was conducted using G*Power v3.1.9.2 to determine the minimum sample size required to find significance with a desired level of power set at 0.80 and alpha (α) level at 0.05. Based on this analysis, it was determined that a **minimum of 205 participants** were required to ensure adequate power for a Pearson's Chi-square Test of Independence. (12, 13, 14)

The anticipated site participants' accrual rate will vary; all sites and participants will be located within the United States. Participants will be recruited from outpatient clinics, larger employers, and/or the general public. Participant recruitment venues are site-specific, for example, outpatient clinic monthly clinical breast exam events. Potential participants will be identified and approached using inclusion/exclusion criteria and site-specific events and/or communication channels.

While exact recruitment methods will be specific to each site, the material will be made available in versions suitable for flyers, email, post through social media, or distributed by mail. Forward-facing participant recruitment materials have been submitted separately with indications on how it can be personalization to each site.

The VIOLA Study participants are all women due to the development and validation of Melody®. The objectives and endpoints encourage minorities, employee volunteers, economically disadvantaged, and/or a medically underserved population to participate in the VIOLA Study. The justification for involving vulnerable populations is because they are primarily affected by disparities in the healthcare system. Employee volunteers are included because study sites provide current medical care and have a trusted relationship with the employee volunteer as a current patient.

Careful considerations have been included in the study design and recruitment process to ensure minimal harm/risks and maximum participant protection. Participants will have access to translated study materials and access to additional healthcare navigation if needed. Employers will not be notified of study participation or Melody® results; participation or nonparticipation is confidential. Each participant will receive a \$25 Walmart gift card when completing the VIOLA Study, and there is no cost to participate.

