10.1 Statistical and Analytical Plans

An a priori power analysis was conducted using G*Power v3.1.9.2 to determine the minimum sample size required to find significance with a desired level of power set at 0.80 and alpha (a) level at 0.05. Based on this analysis, it was determined that a minimum of 205 participants were required to ensure adequate power for a Pearson's Chi-square Test of Independence. (12, 13, 14) (Appendix L)

Each participant will be required to take an enrollment survey that collects information on race, ethnicity, and socio-economic status. Participant's addresses will be obtained as part of the requisition process for the CLIA lab, from which information on geographic location can be obtained. In addition to the factors listed above, the enrollment survey also collects information on status and type of health insurance, reproductive health, breast health knowledge, prior screening history, and family and personal history of cancer.

The exit survey has been designed to collect information on the participant experience with Melody® and comprehension of the information Melody® relayed through their site clinician. In addition, information is collected on participant's intention to schedule/participate in future screening mammograms and/or change in intention to participate in a previously scheduled screening mammogram.

Data will be analyzed using SPSS Statistics software. To determine the presence of significant changes, Unpaired T-tests or Mann-Whitney U-test will be used with a significance level set at P < 0.05.

Due to the effect of COVID-19 on screening rates, screening mammogram participation rates will be compared to rates reported for the state of Arkansas in 2019.

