The results of the power analysis can be found in Table 1 below. Remember that power analysis calculations using lower effect sizes will tell you that you need larger samples, but these are the calculations easiest to justify. The calculations in the H1 hypothesis (percentage difference in compliance between treated and untreated groups) are the initial power calculation. The second calculation under accounting for 10% drop-out, increases the sample size to account for the drop-out rate you requested. Based on the moderate effect size of $\Delta\% = 20\%$ with a power level of .80, we recommend you recruit 205 participants for this study split evenly between treatment and non-treated groups ($N = 103$ each).

Table 1
Minimum Sample Size Needed for Range of Effect Sizes for Each Study Hypothesis

Hypothesis	Power level	Effect Size			
		Effect	Low	Moderate	
H1: Compliance for Treatment vs Untreated groups	$\Delta\%$		10	20	30
Pearson's Chi-square test of Independence	.80	776	186	78	
	.85	886	214	88	
	.90	1038	248	104	
Accounting for 10% drop-out rate	$\Delta\%$		10	20	30
	.80	854	205	86	
	.85	975	235	97	
	.90	1142	273	114	
Minimum sample size	$\Delta\%$		10	20	30
	.80	854	205	86	
	.85	975	235	97	
	.90	1142	273	114	

Note. Alpha level = .05. The numbers represented here are the total number of participants that would be needed for the sample.

Write-up to include in a methods section (if needed)

An a priori power analysis was conducted using G*Power v3.1.9.2 to determine the minimum sample size required to find significance with a desired level of power set at .80, an alpha (α) level at .05. Based on this analysis, it was determined that a minimum of 205 participants (two groups of 103) were required to ensure adequate power for a Pearson's Chi-square Test of Independence. (Cohen, 1988; Erdfelder, Faul, & Buchner, 1996; Faul, Erdfelder, Lang, & Buchner, 2007).

References

Cohen, J. (1988). Statistical power analysis for the behavioral sciences (2nd ed.). Hillsdale, NJ: Lawrence Erlbaum Associates.

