
G*Power Screen-shots

Screenshots

Moderate Effect Size ($\Delta\% = 20$)

Power = .80

Test family	Statistical test		
z tests	Proportions: Difference between two independent proportions		
Type of power analysis			
A priori: Compute required sample size - given α, power, and effect size			
Input Parameters		Output Parameters	
Tail(s)	Two	Critical z	1.9599640
Proportion p2	.70	Sample size group 1	93
Proportion p1	0.5	Sample size group 2	93
α err prob	0.05	Total sample size	186
Power (1- β err prob)	.80	Actual power	0.8000056
Allocation ratio N2/N1	1		

Power = .85

Test family	Statistical test		
z tests	Proportions: Difference between two independent proportions		
Type of power analysis			
A priori: Compute required sample size - given α, power, and effect size			
Input Parameters		Output Parameters	
Tail(s)	Two	Critical z	1.9599640
Proportion p2	.70	Sample size group 1	107
Proportion p1	0.5	Sample size group 2	107
α err prob	0.05	Total sample size	214
Power (1- β err prob)	.85	Actual power	0.8527234
Allocation ratio N2/N1	1		

Power = .90

Test family	Statistical test		
z tests	Proportions: Difference between two independent proportions		
Type of power analysis			
A priori: Compute required sample size - given α, power, and effect size			
Input Parameters		Output Parameters	
Tail(s)	Two	Critical z	1.9599640
Proportion p2	.70	Sample size group 1	124
Proportion p1	0.5	Sample size group 2	124
α err prob	0.05	Total sample size	248
Power (1- β err prob)	.90	Actual power	0.9000032
Allocation ratio N2/N1	1		

N. Namida Lab, Inc. Policies for PHI Use and Disclosures (HIPAA)

POLICIES AND PROCEDURES FOR PHI USE AND DISCLOSURES

INTRODUCTION

These policies and procedures address handling, safeguarding, using, and disclosing protected health information (PHI). Under HIPAA, covered entities must ensure the privacy of a patients' protected health information.

PHI refers to all information (oral, paper-based documents, and electronic documents) that relates to an individual including but not limited to:

- Medical information
- Billing information
- Financial information
- Names and other identifying information such as:
 - Telephone numbers
 - Fax numbers
 - Electronic Mail addresses

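### Appendix L allows for 10% drop-out by multiplying by 1.10 instead of dividing by 0.90, so on its own two-group terms 205 recruits fall slightly short; a minor numerical error

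*Protocol*

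**What the plan says.** The sample size is derived in Appendix L (Power Analysis). The G*Power output for the chosen row shows "Proportion p1 0.5" and "Proportion p2 .70", two tails, alpha 0.05 and equal allocation. It returns 93 per group, 186 in total, with an actual power of 0.8000056.

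The text then describes a second step: "The second calculation under accounting for 10% drop-out, increases the sample size to account for the drop-out rate you requested". Table 1 labels these rows as accounting for a 10% drop-out rate. For the 20-point difference at power 0.80 the row reads 205, and the report concludes: "we recommend you recruit 205 participants for this study split evenly between treatment and non-treated groups", giving 103 for each group. The suggested methods wording at the end of the report repeats 205 as two groups of 103.

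The protocol body carries 205 forward as a minimum. Section 10.1 says that "a minimum of 205 participants were required to ensure adequate power" for a Pearson chi-square test and points to Appendix L. Section 5.3 makes the same statement without that pointer. Neither section mentions drop-out.

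**The concern.** An allowance for drop-out should leave the required number after the stated fraction has been lost. If a fraction d is lost, the number to recruit is N / (1 - d). Multiplying by (1 + d) always gives too few, because (1 + d)(1 - d) = 1 - d². At d = 0.10 that is 0.99, so every total that has not been rounded ends 1% short of its own target.

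The base size has no slack: 186 is the smallest equal-group total that reaches 0.80. Any shortfall in the allowance therefore takes power below the stated level. At stake is whether the study's enrolment figure has the property claimed for it in Appendix L, namely 0.80 power after 10% drop-out.

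**Working it through.** **Inputs (all from Appendix L).** p1 = 0.50, p2 = 0.70, two-sided alpha 0.05 (z = 1.960), power 0.80 (z = 0.842), allocation 1:1, drop-out 10%.

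**Step 1: reproduce the base size.** Two-proportion z test, pooled variance under the null hypothesis, no continuity correction, mean proportion 0.60:

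n per group = [1.960 × √(2 × 0.60 × 0.40) + 0.842 × √(0.50 × 0.50 + 0.70 × 0.30)]² / 0.20²

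= [1.358 + 0.571]² / 0.04 ≈ 93.0, so 93 per group and 186 in total. This matches the appendix. The other eight base sizes in Table 1 also reproduce, with p1 = 0.50 and p2 = 0.60, 0.70 or 0.80. For the 10- and 30-point columns p1 = 0.50 is inferred, since only the 20-point output is shown.

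**Step 2: reproduce the drop-out rows.**

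| Power | Difference | Base N | Base × 1.10 | Printed | Base / 0.90 | Rounded up |
|---|---|---|---|---|---|---|
| 0.80 | 10 | 776 | 853.6 | 854 | 862.2 | 863 |
| 0.80 | 20 | 186 | 204.6 | 205 | 206.7 | 207 |
| 0.80 | 30 | 78 | 85.8 | 86 | 86.7 | 87 |
| 0.85 | 10 | 886 | 974.6 | 975 | 984.4 | 985 |
| 0.85 | 20 | 214 | 235.4 | 235 | 237.8 | 238 |
| 0.85 | 30 | 88 | 96.8 | 97 | 97.8 | 98 |
| 0.90 | 10 | 1038 | 1141.8 | 1142 | 1153.3 | 1154 |
| 0.90 | 20 | 248 | 272.8 | 273 | 275.6 | 276 |
| 0.90 | 30 | 104 | 114.4 | 114 | 115.6 | 116 |

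All nine printed values equal base × 1.10 rounded to the nearest whole number. None equals base / 0.90 rounded up. For two equal groups at the chosen row, 93 / 0.90 = 103.3, so 104 per group and 208 in total.

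**Step 3: what 205 delivers in this model.**
- After 10% loss: 205 × 0.90 = 184.5, which is 1.5 below 186.
- Power with 92.25 per group (184.5 in total): 0.797. With 92 per group (184): 0.796. With 93 per group (186): 0.800.
- Largest loss that still leaves 186: 1 - 186/205 = 9.3%.

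**Step 4: the split.** 2 × 103 = 206, not 205, and 205 is odd, so it cannot be split evenly. With 206 recruited, 206 × 0.90 = 185.4 remain, power is 0.799, and the tolerable loss is 1 - 186/206 = 9.7%. This is closer, but still under 186.

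**The case against.** The best defence is that nothing of consequence turns on this. The corrected total is two women above 205, about 1%. Power of 0.797, or 0.799 with 103 per group, rounds to 0.80. The protocol states 205 as a minimum, so recruitment may exceed it. The group size of 103 is 102.5 rounded up to a whole person. All of this stands as a judgement of size. It does not make the table right: the rows are labelled as allowing for 10% loss and give minimum sizes, and they do not meet that description.

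Three stronger readings are tempting, and the documents do not support them.

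- **That the study is underpowered for this reason.** The loss is under half a percentage point. The larger head-count gaps in the 10-point column (9 to 12 women) are the same 1% of bigger totals, in rows that the study did not choose.
- **That sections 5.3 and 10.1 are false.** They claim adequate power from a minimum of 205 and do not mention drop-out. In Appendix L's model, 205 women analysed give power 0.837, so the sentence is not wrong in itself. It only fails to say that 205 is a recruitment figure. Section 10.1 refers the reader to Appendix L, where this can be seen; section 5.3 does not.
- **That this study must retain 186 women.** In Appendix L, 186 is 93 treated plus 93 untreated. Section 4.1 gives Melody to every participant, and section 10.1 compares participation with 2019 Arkansas rates. The women remaining after drop-out would all be exposed, so 186 is not an analysis target for this cohort.

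**Conclusion.** The error is real but minor. The drop-out rows of Table 1 use the wrong inflation, and at the stated 10% loss 205 gives power of about 0.796 to 0.797 where 0.80 is claimed. The stated 205 and the two groups of 103 also disagree by one.

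This rests on Appendix L's own terms: two equal groups, 50% against 70%, two-sided alpha 0.05, and a 10% loss spread evenly over the groups. It does not address whether a two-group calculation suits a single exposed cohort compared with historical rates. That mismatch is a separate and larger issue, and correcting the inflation does not settle it.

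**What to change.** In Appendix L, do one of two things:

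- recompute the drop-out rows as base / 0.90 rounded up: 863, 207 and 87 at power 0.80; 985, 238 and 98 at 0.85; 1154, 276 and 116 at 0.90, with 208 for two equal groups at the chosen row; or
- keep 205 and state that it allows for about 9% drop-out, with power of about 0.797 at 10%.

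Whichever is chosen, make the total and the per-group figure agree. Where 205 (or its replacement) is quoted in sections 5.3 and 10.1, add that it is a recruitment figure that already includes a drop-out allowance. Do not carry 186 into those sections as the number needed at analysis, because it describes two groups that the study does not enrol.

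The cost is a text and table correction. Under the first option the minimum rises by two or three women; under the second it does not change, and the stated property becomes slightly less favourable.
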